3.8.2. QTc Stopping Criteria

If a subject meets the QTc¹ interval duration criteria below, study treatment(s) will be withheld.

- QT interval corrected for heart rate (HR) by Fredericia's formula (QTcF) >530 msec

¹Based on average QTc value of triplicate ECGs to include manual over-read. For example, if an ECG demonstrates a prolonged QT interval, obtain 2 additional ECGs over a brief period (e.g., within approximately 10 minutes of the abnormal ECG, if possible, and approximately 10 minutes apart from each other), and then use the averaged QTc values of the 3 ECGs to determine whether the subject should have study treatment(s) withheld.

If the QTc prolongation resolves to Grade 1 or baseline, the subject may be re-started on the study treatment(s) if the investigator and GSK Medical Monitor agree that the subject will benefit from further treatment.

Refer to [Appendix 2](#) for country-specific QTc stopping criteria.

3.8.3. Left Ventricular Ejection Fraction (LVEF) Stopping Criteria

3.8.3.1. LVEF Stopping Criteria

Echocardiography (ECHO) or multi gated acquisition scan (MUGA) must be performed at Screening and as outlined in the Time and Events Tables (Section 7.1). Subjects who have an asymptomatic, absolute decrease of >15% in LVEF compared with baseline or an absolute decrease of >10% in LVEF compared with baseline and the ejection fraction is below 50% should temporarily discontinue GSK2849330 and have a repeat evaluation of LVEF within 1 week. ECHO should be repeated every 1 to 2 weeks for 4 weeks or until LVEF recovery to within 15% of baseline or to above 50% and within 10% of baseline depending on which stopping criteria above were met.

- If the LVEF recovers (defined as absolute decrease $\leq 15\%$ compared to baseline or $\geq 50\%$ and absolute decrease $\leq 10\%$ compared with baseline) at any time during the next 4 weeks, after consultation and approval of the GSK Medical Monitor, the subject may be restarted on GSK2849330 at a reduced dose. For such subjects, monitoring of LVEF will be performed 2, 4, and 8 weeks after rechallenge, and then per protocol.
- If repeat LVEF does not recover within 4 weeks, treatment with GSK2849330 should be permanently discontinued. Ejection fraction should be monitored every 4 weeks for a total of 16 weeks or until resolution.

Subjects with Grade 3 or 4 (symptomatic) left ventricular systolic dysfunction must discontinue treatment with GSK2849330. Ejection fraction should be monitored every 4 weeks for a total of 16 weeks or until resolution. If recovery occurs (LVEF $\geq 50\%$ and

symptom resolution) within 4 weeks, treatment with GSK2849330 may be restarted at a reduced dose if the subject is receiving clinical benefit and in consultation with the GSK Medical Monitor.

Copies of all ECHOs/MUGAs and cardiology consultations performed on subjects who experience a >15% decrease in LVEF from baseline or >10% decrease in LVEF from baseline and whose cardiac ejection fraction is < 50% will be required by GSK for review. Instructions for submitting qualifying ECHOs are provided in the SPM.

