7.3.5. Echocardiogram and/or Multi-gated Acquisition (MUGA) Scans

ECHO will be performed to assess cardiac ejection fraction as noted in the Time and Events Tables Section 7.1. Should electrocardiography not be available or if echocardiographic analysis of LVEF is unable to be obtained due to technical factors, a MUGA scan may be performed. However, whichever method is used at baseline should be used for the remaining assessments in the study. Additional ECHO assessments may be performed if clinically warranted. The evaluation of the echocardiographer should include an evaluation for LVEF.

Copies of all ECHOs performed on subjects who experience an absolute decrease >15% in LVEF compared to baseline or an absolute decrease >10% in LVEF compared to baseline concurrent with LVEF <50% may be required by GSK for review.

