- All events of possible study treatment-induced liver injury with hyperbilirubinemia defined as ALT ≥ 3 times ULN **and** bilirubin ≥ 2 times ULN ($>35\%$ direct) (or ALT ≥ 3 times ULN and INR >1.5 , if INR is measured) or termed ‘Hy’s Law’ events (INR measurement is not required and the threshold value stated will not apply to subjects receiving anticoagulants).

NOTE: Bilirubin fractionation is performed if testing is available. If testing is not available, record presence of detectable urinary bilirubin on dipstick indicating direct bilirubin elevations and suggesting liver injury. If testing is unavailable and a subject meets the criterion of total bilirubin ≥ 2 times ULN, then the event is still reported as a SAE. If INR is obtained, include values on the SAE form. INR elevations >1.5 suggest severe liver injury.

- LVEF (Section 3.8.3.1): meeting stopping criteria.

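### The LVEF restart bullet in Protocol Section 3.8.3.1 omits the clause that ties each recovery limb to its hold criterion, so read literally an unchanged repeat ECHO below 50% can count as recovery

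*Protocol*

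**What the plan says.** All the operative text is in Protocol Section 3.8.3.1.

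- **Hold.** An asymptomatic subject stops temporarily for an absolute LVEF fall of more than 15 points (first criterion), or under the second: "an absolute decrease of >10% in LVEF compared with baseline and the ejection fraction is below 50% should temporarily discontinue GSK2849330". A repeat LVEF is due within 1 week.
- **Repeat ECHOs.** These continue every 1 to 2 weeks for 4 weeks or until LVEF returns to within 15 points of baseline, or "to above 50% and within 10% of baseline depending on which stopping criteria above were met".
- **Restart bullet.** It opens "If the LVEF recovers (defined as absolute decrease" and gives its own definition: a decrease of at most 15 points, or LVEF of at least 50% with a decrease of at most 10 points, at any time in the next 4 weeks. Then, "after consultation and approval of the GSK Medical Monitor, the subject may be restarted on GSK2849330 at a reduced dose". LVEF is rechecked 2, 4 and 8 weeks after rechallenge.
- **Discontinuation bullet.** Treatment stops permanently if LVEF does not recover within 4 weeks.
- **Symptomatic rule.** For Grade 3 or 4 dysfunction the restart condition begins "If recovery occurs (LVEF" and requires at least 50% plus symptom resolution.

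Elsewhere, entry excludes LVEF below 50% (Section 5.2.5, criterion 7). Section 8.2 makes LVEF "meeting stopping criteria" a protocol-specific SAE, and Section 8.5 has SAEs reported to the sponsor within 24 hours.

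**The concern.** The two limbs in the restart bullet are joined by a bare "or", and the clause assigning each limb to its hold criterion is not repeated. The looser limb therefore appears open to every held subject, including one held because LVEF fell below 50%.

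The bullet governs re-dosing, and the next bullet uses the same notion of recovery to decide permanent discontinuation. If the definition is too generous, both decisions move the same way: a subject still meeting a cardiac hold criterion may be put forward for restart, and the 4-week discontinuation rule does not catch that subject.

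**Working it through.** The plan gives no figure to reproduce. This is a logic check, followed by a count to show its extent.

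**Inputs** (Section 3.8.3.1; entry floor from Section 5.2.5). Let B be baseline LVEF and L the current LVEF, in percentage points, with B ≥ 50.

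- H1 (first hold criterion): B − L > 15
- H2 (second hold criterion): B − L > 10 and L < 50
- R1 (first recovery limb): B − L ≤ 15
- R2 (second recovery limb): L ≥ 50 and B − L ≤ 10

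**Step 1: the second limb is redundant.** A decrease of at most 10 is also a decrease of at most 15, so R2 implies R1. The literal rule "R1 or R2" reduces to R1, and its 50% floor has no effect.

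**Step 2: R1 overlaps H2.** Both hold whenever 10 < B − L ≤ 15 and L < 50. In whole numbers that is a fall of 11 to 15 points with LVEF below 50%.

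**Step 3: example.** Baseline 60, hold at 48, repeat ECHO 48. The fall is 60 − 48 = 12 and 48 < 50, so H2 is still met. R1 is true (12 ≤ 15) and R2 is false. The literal bullet calls this recovered. With the limb matched to the criterion, R2 is required and the subject has not recovered.

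**Step 4: extent.** Whole-number baselines 50–75, with hold and repeat values from 10 up to baseline. A conflict is a hold/repeat pair in which the repeat counts as recovered but still meets H1 or H2.

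| Criteria met at hold | Literal bullet | R1 required if H1 was met, R2 if H2 was met |
|---|---|---|
| H2 only | 305 of 3,060 | 0 |
| H1 only | 0 of 3,465 | 0 |
| Both | 2,020 of 50,160 | 0 |

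In all, 0 of 3,060 + 3,465 + 50,160 = 56,685 pairs conflict under the matched rule.

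The overlapping readings number five at each baseline from 50 to 60, then 4, 3, 2 and 1 at baselines 61 to 64, and none from 65. For H2-only holds the conflicting pairs are these counts squared: 11 × 25 + 16 + 9 + 4 + 1 = 305. The lowest repeat LVEF accepted is 35 at baseline 50, 40 at 55 and 45 at 60.

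**Step 5: holds that met both criteria.** Every fall of more than 15 points from a baseline of 50 to 65 also leaves LVEF below 50, so it meets H1 and H2 together. Example: baseline 62, hold at 45 (fall 17), repeat 48 (fall 14). R1 alone accepts this repeat although H2 is still met; requiring both limbs rejects it. Neither sentence expressly says which applies.

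**The case against.** The strongest reply is that the intent is plain. The sentence just before the bullet uses the same two limbs in the same order and ties them to the criteria met. A reading that leaves the second limb with no work to do is itself suspect. When both criteria were met, the plural in "to above 50% and within 10% of baseline depending on which stopping criteria above were met" naturally calls for both limbs. This stands as evidence of intent. It does not repair the bullet, which carries its own definition and does not refer back; the earlier sentence governs how long ECHOs are repeated.

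It can also be said that the hold instruction is not limited to the first occurrence, so a subject still meeting it should remain off drug whatever a permissive bullet allows. Section 3.9.4 also delays dosing for clinically significant drug-related toxicity until Grade 1 or baseline. Both support caution, but neither defines LVEF recovery, and Section 3.9.4 is not specific to LVEF.

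The safeguards are real. Restart is optional, needs Medical Monitor approval, is at a reduced dose and is followed by three timed checks. The event is an SAE reported within 24 hours. The sponsor also has a route to the scans: Section 3.8.3.1 requires "Copies of all ECHOs/MUGAs and cardiology consultations performed on subjects who experience a >15% decrease in LVEF from baseline" (or who meet the second criterion), although Section 7.3.5 says of the same ECHOs only "concurrent with LVEF <50% may be required by GSK for review".

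A reader might infer that every second-criterion-only subject is already recovered on the reading that triggered the hold. The documents do not support that. A repeat is required within 1 week and recovery is judged during the following 4 weeks, so a later ECHO decides. The supportable statement is that an unchanged later ECHO would pass. The entry floor and the symptomatic rule cover different situations; they show that 50% is a threshold the protocol uses, not that it fixes the asymptomatic restart level.

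**Conclusion.** The point holds as a wording error in a re-dosing rule. Followed literally, the restart bullet treats a repeat LVEF that still meets the second hold criterion as recovery, and the 4-week discontinuation rule then does not apply.

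It is minor. The intended rule can be recovered from the adjacent sentence, the safeguards make an inappropriate restart unlikely, and no endpoint or analysis is affected.

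The logical conclusion depends only on the stated thresholds. The counts rest on whole-number LVEF and an assumed range of values; they describe the reach of the wording, not how often a subject would be affected. It would go too far to say that the protocol intends restart below 50%, or that subjects meeting both criteria face contradictory rules. For them the text is silent, and the natural reading gives the right result.

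**What to change.** Use one definition in both the repeat-ECHO sentence and the restart bullet:

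- If the second criterion (fall of more than 10 points with LVEF below 50%) was met, alone or with the first, recovery requires LVEF ≥50% and a decrease from baseline of ≤10 points on a repeat ECHO.
- If only the first criterion (fall of more than 15 points) was met, recovery requires a decrease from baseline of ≤15 points on a repeat ECHO.

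As a tidy-up, write ≥50% in both places; the repeat-ECHO sentence now says above 50%. Keep Medical Monitor approval, the reduced dose and the 2-, 4- and 8-week checks.

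The cost is one reworded definition in one section, with no new assessment or data.

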3.9. Guidelines for Events of Special Interest and Dose Modifications

The severity of AEs will be graded utilizing NCI-CTCAE, version 4.0 [NCI, 2009]. Guidelines for dose modifications and interruptions for management of common toxicities associated with the study treatment(s) are provided in this section.

In subjects experiencing suspected infusion-related reactions, a whole blood sample for selected cytokines (including but not limited to TNF alpha, IL-6, and tryptase) should be drawn within 24 hours and submitted to the central laboratory for analysis (see SPM for instructions).

3.9.1. Management of Infusion Reactions

As there is a risk of infusion reactions during administration of IV immunoglobulins, including monoclonal antibodies, subjects will be monitored for signs and symptoms of an infusion-related reaction (including Grade 1 to 2 fever, chills, headache, nausea, malaise) during infusion and for a minimum of 1 hour after the first administration of GSK2849330.

If an infusion-related reaction occurs during administration, the infusion rate may be reduced or halted at the discretion of the investigator and/or GSK medical monitor, depending on the severity of the symptoms and the subject will receive appropriate medical treatment. For subsequent infusions, the investigator may provide premedication with antihistamines, acetaminophen, and/or corticosteroids and may reduce the starting infusion rate.

Treatment may include:

- **Fevers/Myalgia:** Initiate treatment with acetaminophen (paracetamol). If subject's fever does not respond to acetaminophen, consideration should be given to the use of a nonsteroidal anti-inflammatory drug (NSAID) such as indomethacin. Consider pre-medication with acetaminophen for subsequent doses.
- **Chills/rigors:** Use warming blankets as initial intervention; consider IV meperidine (pethidine) if chills persist.
- **Nausea/vomiting:** Consider treatment with 5-HT3 antagonists, prochlorperazine, lorazepam; some agents may cause hypotension and altered mental status; therefore, these agents should be used with caution.

3.9.2. Allergic Reaction Monitoring and Management

As GSK2849330 is a fully humanized antibody, it is considered unlikely for acute allergic reactions to occur in response to GSK2849330 exposure; however, all subjects will be monitored carefully for evidence of allergic response. A subject that exhibits signs or symptoms of severe hypersensitivity or anaphylaxis will receive appropriate medical treatment and remain on study at the discretion of the investigator and after discussion with the GSK medical monitor.

In accordance with the preparedness for treatment of anaphylaxis, emergency resuscitation equipment, advanced cardiac life support equipment, and medications must be readily accessible during GSK2849330 administration.

It is important to recognize early signs of an anaphylaxis reaction and appropriate treatment must begin immediately to prevent progression to severe anaphylaxis. Subjects will be closely monitored in an appropriate setting for early signs of dyspnea and edema. Antihistamines, such as diphenhydramine; and corticosteroids such as prednisolone may be given to reduce symptoms.

If more severe clinical signs arise, immediate assessment of the ABC's (airway, breathing, and circulation from Basic Life Support) will be done in all suspected anaphylactic reactions. Cardio-Pulmonary Resuscitation (CPR) will be initiated if needed. Epinephrine will be given by injection without delay. Emergency interventions may include endotracheal intubation or tracheostomy. Treatment for shock will include IV fluids and medications that support the actions of the heart and circulatory system.

3.9.3. Diarrhea Management

If episodes of diarrhea occur, causes for the diarrhea other than the study treatment such as concomitant medications (e.g., stool softeners, laxatives, antacids, etc.), infections by *Clostridium. difficile* or other pathogens, partial bowel obstruction, etc., should be ruled out. Subjects should be instructed to first notify their physician/healthcare provider at onset of diarrhea of any severity. Supportive measures depend on the severity of the diarrhea and could include the following as clinically indicated:

- Dietary modifications (e.g. small, frequent meals, low fiber, and lactose-avoidance; addition of foods rich in potassium)
- Maintain hydration with clear liquids or IV fluids as needed
- Loperamide and/or oral antibiotics
- Second-line agents
- Hold GSK2849330

Additional recommended guidelines for the treatment of study treatment induced diarrhea are provided in Benson, et.al. [[Benson, 2004](#)] and in [Appendix 9](#).

3.9.4. Dose Modifications

In the event of a toxicity that meets the guidelines for DLT (Section 3.3.1) or is otherwise considered to be clinically significant by the treating physician, treatment will be stopped and supportive therapy administered as clinically indicated. If clinically significant drug-related toxicity is present, treatment should be delayed until the toxicity resolves (with or without supportive therapy) to baseline or \leq Grade 1. If the toxicity does not resolve to \leq Grade 1 or baseline within 2 weeks, withdrawal from the trial is recommended unless otherwise agreed to by a GSK Medical Monitor and the investigator based on evidence of clinical benefit.

For subjects enrolled in the 30 mg/kg weekly dosing cohort, the dosing frequency may be reduced to every 2 weeks at the discretion of the investigator for a toxicity that does not automatically necessitate a dose reduction.

3.9.5. Dose Reductions

Part 1: A subject who experiences a toxicity at any time during treatment with GSK2849330 that either meets the guidelines for DLT (Section 3.3.1) or is otherwise considered to be clinically significant by the treating physician, should have their dose reduced to the previously tested next lower dose level. Any subject who experiences one or more recurrent clinically significant toxicities after the initial dose reduction may have one further dose reduction except where noted otherwise. Subjects who continue to experience clinically significant toxicity despite two dose reductions (i.e., unacceptable toxicity) will be discontinued from the study.

Part 2: Subjects who begin the selected dose and require a dose reduction (due to tolerability/toxicity issues), should be dose reduced to one level below the recommended Part 2 dose. Further dose reductions should be discussed with the GSK Medical Monitor.

4. INVESTIGATIONAL PRODUCT(S)

The term ‘study treatment’ is used throughout the protocol to describe the investigational product (IP) received by the subject as per the protocol design. The study was initiated with vials containing 1 mL of IP. Vials containing 5 mL were later introduced, and for the remainder of the study, both 1-mL and 5-mL vials will be available.

4.1. Description of Investigational Product(s)

Product name :	GSK2849330 solution for infusion 100 mg/mL
Formulation description:	Solution containing 100 mg/mL GSK2849330 in vials containing 1 mL for injection or Solution containing 100 mg/mL GSK2849330 in vials containing 5 mL for injection
Dosage form :	Solution for Infusion. The solution is stored at 2-8°C.
Unit dose strength(s)/Dose Level(s):	IV/100 mg/mL (refer to Section 3.3 and Section 3.4 for dose levels)
Physical Description:	GSK2849330 solution for infusion is clear to opalescent, pale yellow or pale brown in color.
Route/ Administration/ Duration:	Delivered as an IV solution (see Section 3.7.2).
Dosing instructions:	Dilute GSK2849330 solution into a 0.9% sodium chloride IV bag to the appropriate concentration for the dose. Deliver the entire contents of the IV bag to the subject.
Manufacturer/ Source of Procurement:	GSK

GSK2849330 will be provided to sites by GSK. The contents of the label will be in accordance with all applicable regulatory requirements.

4.2. Preparation/Handling/Storage of GSK2849330 GSK Investigational Product

Preparation

Dilute GSK2849330 solution into a 0.9% sodium chloride IV bag to the appropriate concentration for the dose. Deliver the entire contents of the IV bag to the subject. The administration kits can be polymerizing vinyl chloride (PVC) or polyolefin (PO) plastics. A 0.22- μ M polyethersulfone (PES) filtration set will be used for this study.

Handling

Under normal conditions of handling and administration, IP is not expected to pose significant safety risks to site staff. A Material Safety Data Sheet (MSDS) describing the occupational hazards and recommended handling precautions will be provided to site staff if required by local laws or will otherwise be available from GSK upon request.

Take adequate precautions to avoid direct eye or skin contact and the generation of aerosols or mists.

In the case of unintentional occupational exposure notify the study monitor, the GSK Medical Monitor and/or the study manager.

Refer to the SPM for detailed procedures for the disposal and/or return of unused study treatments.

Storage

GSK2849330 must be stored in a secure area under the appropriate physical conditions for the product. Access to and administration of the GSK2849330 will be limited to the investigator and authorized site staff. GSK2849330 must be dispensed or administered only to subjects enrolled in the study and in accordance with the protocol.

GSK2849330 is to be stored at a temperature range of 2°C to 8°C. Maintenance of a temperature log (manual or automated) is required.

4.3. Product Accountability

In accordance with local regulatory requirements, the investigator, designated site staff, or head of the medical institution (where applicable) must document the amount of IP dispensed and/or administered to study subjects, the amount returned by study subjects, and the amount received from and returned to GSK, when applicable. Product accountability records must be maintained throughout the course of the study. Refer to the SPM for further detailed instructions on product accountability.

4.4. Treatment Compliance

GSK2849330 will be administered IV to subjects at the study site. Administration will be documented in the source documents and reported in the eCRF.

Treatment start and stop dates, including dates and reasons for treatment delays and/or dose modifications will also be recorded in the dosing eCRF.

4.5. Treatment of Investigational Product Overdose

In the event of an overdose (defined as administration of more than the highest protocol-specified dose) of GSK2849330, the investigator should:

- contact the GSK Medical Monitor immediately
- closely monitor the subject for AEs/SAEs and laboratory abnormalities for at least 45 days or 5 half-lives (whichever is longer) for GSK2849330
- obtain a plasma sample for PK analysis within 30 days from the date of the last dose of study treatment if requested by the GSK Medical Monitor (determined on a case-by-case basis)
- document the quantity of the excess dose as well as the duration of the overdosing in the eCRF.

Decisions regarding dose interruptions or modifications will be made by the investigator in consultation with the GSK Medical Monitor based on the clinical evaluation of the subject.

